## 4.0 OVERVIEW OF STUDY DESIGN/INTERVENTION

### 4.1 Design

**Phase Ib:** The phase Ib portion of the study is designed to determine the MTD of romidepsin and lenalidomide. All patients must have a relapsed or refractory B-cell lymphoma, T-cell lymphoma, or multiple myeloma. Patients will be treated on a 28-day cycle with romidepsin infused on day 1, 8, and 15, and lenalidomide taken orally on days 1-21. The design is a standard 3+3 dose escalation (Table 1) of romidepsin and lenalidomide. The first cohort will enter at dose level 1.

Dose Level	Romidepsin	Lenalidomide
-1	8 mg/m 	10 mg
1	8 mg/m 	15 mg
2	8 mg/m 	25 mg
3	10 mg/m 	25 mg
4	14 mg/m 	25 mg

Table 1: Description of dose level

DLT is defined in cycle 1 (in phase Ib).

Definitions:

- Grade  $\geq$  3 non-hematologic (attributed to study drugs)
- Grade 4 hematologic toxicities (attributed to study drugs) defined as:
  - Grade 4 thrombocytopenia (platelets  $< 25$  K/ $\mu$ L)
  - Grade 4 neutropenia (absolute neutrophil count (ANC)  $< 0.5$ )
- Grade 3 thrombocytopenia or neutropenia that results in a  $> 3$  day delay in any romidepsin dose in cycle 1.
- One week or greater delay in initiating cycle 2 day 1 due to continued drug-related toxicity.

Any patient with an adverse event that meets the DLT definition is considered evaluable for MTD determination. Patients who do not have a DLT, but received  $<3$  doses of romidepsin or  $<80\%$  (17/21) of the doses of lenalidomide during cycle 1 will not be evaluable for MTD and will be replaced.

Three patients will be initially treated in each cohort until the MTD is determined. If dose level 4 (full dose of each drug) is achieved without DLT after 1 cycle that dose level will be deemed the optimal dose and the study will proceed to a phase IIa expansion cohort. Patients treated at MTD in the phase Ib portion will be counted towards the phase IIa accrual by disease subtype and also for all efficacy and toxicity endpoints unless they did not have measurable disease at point of study entry as allowed in the phase Ib portion.

**Phase IIa:** The phase IIa portion will further assess the toxicity and safety and allow a preliminary assessment of the efficacy of the combination to provide background for a potential future subtype specific phase II study (see Section14.0).

DLT is defined in cycles 1-4 (in phase IIa)

Definitions:

- Grade  $\geq$  3 non-hematologic (attributed to study drugs)

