  - Renal function assessed by calculated creatinine clearance as follows (see Appendix B):
    - Phase Ib subjects must have calculated creatinine clearance  $\geq 50\text{ml/min}$  by Cockcroft-Gault formula.

- Phase IIa subjects must have calculated creatinine clearance  $\geq$  30ml/min by Cockcroft-Gault formula. See section below, "Dosing Regimen", regarding lenalidomide dose adjustment for calculated creatinine clearance  $<$  60ml/min and  $\geq$  30ml/min.
  - Total bilirubin  $\leq$  1.5 x upper limit of normal (ULN); 3 x ULN if due to hepatic involvement.
  - AST (SGOT) and ALT (SGPT)  $\leq$  3 x ULN; 5 x ULN if due to hepatic involvement.
11. All study participants must be registered into the mandatory Revlimid REMS® program, and be willing and able to comply with the requirements of the REMS® program.
12. Females of reproductive potential must adhere to the scheduled pregnancy testing as required in the Revlimid REMS® program. Men must agree to use a latex condom during sexual contact with a FCBP even if they have had a successful vasectomy. See Appendix C: Risks of Fetal Exposure, Pregnancy Testing Guidelines and Acceptable Birth Control Methods.

† A female of childbearing potential is a sexually mature female who: 1) has not undergone a hysterectomy or bilateral oophorectomy; or 2) has not been naturally postmenopausal for at least 24 consecutive months (i.e., has had menses at any time in the preceding 24 consecutive months).

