### **9.7.1 Instructions for Dose Modifications or Interruption During a Cycle**

Dose delay and dose reduction rules for lenalidomide and romidepsin are as follows and summarized in the tables 3, 4, & 5:

- In the event of dose reduction due to hematologic toxicity attributed to study drugs, lenalidomide and romidepsin will be reduced as per Tables 3 & 4.
- In the event of dose reduction due to non-hematologic toxicity attributed to study drugs, lenalidomide and romidepsin will be reduced one level per Tables 3 & 4.
- Missed doses of lenalidomide and/or romidepsin are not made up.
- Interruptions of therapy, including delays in starting a new cycle, of greater than 28 days will result in removal from study.
- Patients remaining on treatment after cycle 6, at the discretion of their physician, may elect to receive romidepsin on a day 1 and 15 schedule each cycle.
  - Patients remaining on treatment after cycle 9, at the discretion of their physician may elect to receive romidepsin on day 1 of each cycle (q4 week dosing) after discussion with the MSK Principal Investigator.
- If a patient is at the lowest dose level and deriving benefit from therapy, they may continue on protocol therapy despite  $\geq$  grade 3 hematologic toxicity or non-clinically significant non-hematologic toxicity after discussion with the MSK principal investigator.

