## **10.0 EVALUATION DURING TREATMENT/INTERVENTION**

### **10.1 A new cycle of treatment may begin on the scheduled Day 1 of a new cycle if:**

- ANC is  $\geq 1.0$  K/ $\mu$ L
- Platelet count is  $\geq 70$  K/ $\mu$ L or within 10 K/ $\mu$ L of baseline.
- Serum creatinine concentration  $\leq 2.0 \times$  ULN or  $\leq$  baseline
- AST (SGOT) and ALT (SGPT)  $\leq 2.0 \times$  ULN or  $\leq 3.0 \times$  ULN in presence of demonstrable liver metastases.
- Serum potassium and magnesium are within normal range.
  - In cycle 2 and beyond in Phase Ib and any cycle in Phase IIa, magnesium and potassium levels may be checked up to 3 days prior to administration of romidepsin. If levels are within range at that time point romidepsin may be administered without recheck unless clinically indicated (such as vomiting, diarrhea, or initiation of medications that may affect electrolytes).
  - Supplements must be given to patients whose potassium and/or magnesium are below normal range.
    - Magnesium supplementation: If levels are below normal range, but  $\geq 1.2$  mg/dL, patients can receive at least 2gm magnesium IV and proceed to treatment without re-checking labs. Patients can be treated if magnesium levels are above normal range.
    - Potassium supplementation: If levels are below normal range, but  $\geq 3.2$  mEq/L, patients can receive at least 20mEq potassium IV and proceed to treatment without re-checking labs.
- Any drug-related maculo-papular rash or neuropathy that may have occurred has resolved to  $\leq$  grade 1 severity
- Any other clinically significant adverse events that may have occurred have resolved to  $\leq$  grade 2 severity.

**If these conditions are not met on Day 1 of a new cycle, the subject will be evaluated weekly and a new cycle of treatment will not be initiated until the toxicity has resolved as described above.**

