**Table 7 Legend**

\* Romidepsin dosing may be delayed up to 3 days of the scheduled visit. Romidepsin doses must be given at least 7 days apart and all doses completed by day 21 of each cycle. In cycle 1, labs may be performed up to 1 day prior to treatment. After completion of cycle 1, labs may be performed up to 3 days prior to treatment.

\*\* For cycle 2 and beyond, study procedures should be performed per the study evaluation schedule ( $\pm 3$  days) while maintaining the minimum dosing spacing for romidepsin as above.

If Physical examination, vital signs, weight and ECOG performance status were done within 7 days of Day 1, they do not need to be repeated at study cycle X, Day 1 (excluding cycle 1 in the phase Ib portion). An unscheduled visit can occur at any time during the study.

The schedule for ECG monitoring is found in section 10.5 and romidepsin dose modifications in Table 6. After cycle 2 the schedule can be amended as clinically indicated in section 10.5.

Sodium, potassium, chloride, bicarbonate, BUN, creatinine, calcium, and glucose are part of the electrolyte assessment at every time point. **Magnesium** will be added to the electrolyte panel at **screening, days 1, 8 and 15 of the treatment cycle, and at the end of study visit**. **Liver function analysis** (at least total protein, albumin, AST,

ALT, alkaline phosphatase, total bilirubin) is necessary on day 1 of each cycle (within windows for labs provided depending on the cycle of treatment). The LDH may be omitted in patients with multiple myeloma.

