 Lymphoma: CT including at least the chest, abdomen and pelvis or PET/CT is required for response (systemic B and T-cell lymphoma patients only) assessment. A bone marrow will only be repeated to confirm a complete response if previously known to be involved. Cutaneous T-cell lymphoma patients will have imaging at baseline and (CTCL) will have an mSWAT (Appendix I) performed monthly for the first three cycles and then at each response assessment timepoints (end of cycle 4, 6 and thereafter at the end of every third cycle). In CTCL patients, imaging will be repeated if appropriate (patients with known nodal or visceral disease) every other cycle. Sezary panel in patients with Sezary syndrome. Cutaneous lymphoma patients without nodal or visceral disease will have imaging repeated only to confirm a complete response. After cycle 12, patients on continuous therapy may be imaged as clinically indicated, at the discretion of the treating physician. At discontinuation of therapy, end of study response assessments – including imaging – should be performed.

Serum/urine protein electrophoresis, serum/urine immunofixation, quantitative immunoglobulins, and serum free light chains are required if appropriate for (multiple myeloma patients only) response assessment. A bone marrow will only be repeated if to confirm a complete response. Patients with non-secretory myeloma will have the bone marrow assessment repeated if they have been otherwise clinically stable (i.e. without new lytic lesions, soft-tissue plasmacytomas or hypercalcemia). A skeletal survey is allowed to rule out bone lesions for evaluation of disease progression and to confirm a complete response in nonsecretory multiple myeloma. PET/CT should be performed at screening and to confirm responses in patients with soft tissue plasmacytomas.

 An additional safety assessment will be done 28 days (+/- 2 days) following the last dose of protocol therapy.

 If romidepsin is omitted on day 8 per dose reduction algorithm (Table 4) then hematologic and electrolyte assessments are not required.

Response assessment will be performed at the end of cycles 2, 4, and 6. Thereafter, response assessment will occur at the end of every third cycle (9,12,15, etc.) until disease progression or removal from study. Myeloma patients will have their disease assessed after each cycle.

 +/- 3 days

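### AST/ALT limits for starting a new cycle are stricter than the entry limits and have no baseline allowance, so a stable eligible patient can be removed without new toxicity or progression

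*Combined protocol and SAP*

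**What the plan says.** **Entry.** Section 6.1, criterion 10, sets the AST and ALT ceiling at "3 x ULN; 5 x ULN if due to hepatic involvement".

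**New cycle.** Section 10.1 requires AST and ALT at or below 2.0 x ULN, or at or below 3.0 x "ULN in presence of demonstrable liver metastases". In the same list, creatinine may be at or below 2.0 x ULN or no higher than baseline, and platelets may be at least 70 K/µL or within 10 K/µL of baseline.

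**If a condition fails.** Section 10.1 continues: "If these conditions are not met on Day 1 of a new cycle, the subject will be evaluated weekly", and the cycle is withheld until resolution to the listed limits.

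**Removal.** Section 9.7.1: "Interruptions of therapy, including delays in starting a new cycle, of greater than 28 days will result in removal from study".

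**Timing.** The Table 7 legend says that liver function analysis "is necessary on day 1 of each cycle". Section 10.2, which governs the later romidepsin doses within a cycle, sets no AST/ALT limit.

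**The concern.** The protocol accepts a transaminase level at entry and then treats the same level as a bar to the next cycle. A relapsed or refractory patient whose value has not moved could lose treatment after one cycle, with neither toxicity nor progression.

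The neighbouring lines suggest an oversight. The platelet line's baseline allowance accommodates patients admitted at 50 K/µL because of marrow involvement. AST/ALT has a similar disease-related allowance at entry but nothing to match it at re-treatment.

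The two sections also use different terms. Criterion 10 speaks of hepatic involvement and section 10.1 of liver metastases. If a site does not count lymphoma or myeloma in the liver as metastases, the conflict for those patients starts at 2.0 rather than 3.0 x ULN.

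For the analysis, an early removal could cost a later response. It could also lead to an EFS event if another therapy follows, because section 4.1 counts a change in therapy as an event.

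**Working it through.** The plan gives no figure for this point. The check sets the limits side by side, follows the calendar, and then sizes the effect for one hypothetical patient.

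**1. The gap**

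| Patient | Entry limit (6.1) | New-cycle limit (10.1) | Eligible but blocked |
|---|---|---|---|
| No hepatic involvement | 3 x ULN | 2.0 x ULN | >2.0 to 3.0 |
| Hepatic involvement, counted as liver metastases | 5 x ULN | 3.0 x ULN | >3.0 to 5.0 |
| Hepatic involvement, not so counted | 5 x ULN | 2.0 x ULN | >2.0 to 5.0 |

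**2. The calendar.** With 28-day cycles, cycle 2 is due on day 29. Weekly rechecks fall on days 36, 43, 50 and 57. On day 57 the delay is 57 − 29 = 28 days, which is not yet more than 28; it exceeds 28 from day 58. A patient is removed if all five checks fail.

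**3. Existing exceptions.** Section 9.7.1 lets a patient at the lowest dose level who is benefiting continue despite non-clinically significant non-hematologic toxicity, after discussion with the MSK principal investigator. That does not reach a patient at a starting dose and does not alter the 10.1 limits. A prospective deviation (section 16.3) needs IRB/PB approval each time.

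**4. Size for one patient, current rule.** Assumptions, none from the documents: one analyte, no trend, independent lognormal values with mean M = 2.5 x ULN and within-patient CV of 10% to 20%.

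σ = √ln(1 + CV²); P(one check above 2.0) = Φ[(ln M − σ²/2 − ln 2.0)/σ]; P(all five) is its fifth power.

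- CV 10%: σ = 0.0998; Φ(2.19) = 0.986; 0.986⁵ ≈ 0.93.
- CV 20%: σ = 0.198; Φ(1.03) = 0.848; 0.848⁵ ≈ 0.44.

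Taking 2.5 as the median instead gives 0.94 and 0.50.

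**5. Same patient with *or ≤ baseline*.** The limit becomes the patient's own entry value. Simulating 1,000,000 patients, keeping those with a baseline above 2.0 and up to 3.0, gives about half held on the scheduled day 1. All five checks fail in about 16% (CV 10%) and 9% (CV 20%). As a rough check that ignores the entry restriction: for exchangeable values the first recheck exceeds baseline with probability 1/2, and all five exceed it with probability 1/6 = 0.167.

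**6. Sensitivity to the assumed level.** Under the current rule, moving the level from 2.1 to 2.9 x ULN, with CV 10% to 20%, moves the removal probability from about 5% to nearly 100%. The 2.5 x figures are therefore an illustration, not an estimate. The hepatic group (>3.0 to 5.0) was not simulated.

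**The case against.** **Stricter re-treatment limits may be deliberate.** Entry and re-treatment limits do different jobs, and both drugs list liver test abnormalities (sections 11.1, 11.2 and 11.4). This is a fair point: a difference between the two limits is not in itself an error. But the protocol gives no reason for withholding a baseline allowance from this line, and blocking a patient on an unchanged, accepted value is a poor way to guard against drug-induced liver injury. With no AST/ALT limit on days 8 and 15, the bar also operates only at the start of a cycle.

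**A baseline elevation is not a toxicity.** Section 10.1 does speak of toxicity resolving, so a site might let the patient proceed. The trigger, however, is failure of the listed conditions, and the AST/ALT condition is absolute. If sites could read it both ways, that supports clarifying it.

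**A reader might infer that such patients can never start treatment.** One sub-bullet of 10.1 says "In cycle 2 and beyond in Phase Ib and any cycle in Phase IIa", and Table 7 schedules liver tests on cycle 1 day 1. The documents do not support this reading. The sub-bullet concerns only how early electrolytes may be checked, and it recurs in section 10.2. Table 7 schedules a test, not a threshold. Section 10.1 governs a new cycle and looks to resolution of toxicity, which presupposes earlier treatment.

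**A reader might infer material damage to the response results, especially in the six added acute T-cell leukemia/lymphoma patients.** That would require an affected patient to be enrolled there and to be unable to respond. Neither is known. The patient would have received cycle 1, and the Table 7 legend requires assessment: "At discontinuation of therapy, end of study response assessments", imaging included; myeloma is assessed after every cycle. The zero-response probability in section 14.0 is descriptive and carries no decision rule.

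**A reader might prefer re-treatment up to the entry ceiling.** That would hold fewer stable patients, but a patient with hepatic involvement at 3.1 x ULN could rise to 5.0 on treatment and still be re-dosed. The documents give no basis for that safety trade.

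**Conclusion.** The conflict is real and stands in the current text; no other provision resolves it for AST/ALT. Followed exactly, the plan can remove a stable, eligible patient after one cycle without new toxicity or progression. Severity is low.

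The textual mismatch is certain, but its impact is not. How many patients enter in the gap is not stated and may be zero. Any removal probability rests on an assumed level, an assumed variation and no trend; a value raised by liver disease could fall with response.

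The consequences reach individual patients' access to treatment and the secondary, descriptive endpoints. A reader might infer that the MTD objective is also compromised, because a delayed cycle 2 can count as a DLT. Section 4.1 limits that item to "One week or greater delay in initiating cycle 2 day 1 due to continued drug-related toxicity", and a stable pre-treatment elevation is not drug-related.

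**What to change.** In section 10.1, add *or ≤ baseline* to the AST/ALT line, as the creatinine line already has, and replace liver metastases with hepatic involvement so that the term matches criterion 10.

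The cost is one edited line, with no added tests, visits or patients. There are two downsides. Dosing would continue at a transaminase level equal to the patient's own baseline. Some stable patients would still be held through ordinary fluctuation: about half on the scheduled day 1 in the 2.5 x ULN illustration, mostly briefly, with about 16% to 9% still removed. That residue would be larger for a patient whose usual level lies near 3.0, since the entry ceiling selects baselines below that level.

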## 6.2 Subject Exclusion Criteria

1. Patients who have a standard curative option for their lymphoid malignancy at current state of disease are excluded. For eligibility on this trial, allogeneic stem cell transplantation is not to be considered a standard curative option.
2. Any serious medical condition, laboratory abnormality, or psychiatric illness that would prevent the subject from signing the informed consent form.
3. Pregnant females. (Lactating females must agree not to breast feed while taking lenalidomide or romidepsin).
4. Known hypersensitivity to thalidomide.
5. The development of erythema nodosum if characterized by a desquamating rash while taking thalidomide or similar drugs.
6. Prior use of lenalidomide if discontinued due to toxicity.
7. Prior therapy with romidepsin if discontinued due to toxicity.
8. Concurrent use of other anti-cancer agents or treatments.
9. Known seropositive and requiring anti-viral therapy for human immunodeficiency virus (HIV), hepatitis B virus (HBV) or hepatitis C virus (HCV).

10. Active concurrent malignancy requiring active therapy.
11. Known central nervous system or meningeal involvement (in the absence of symptoms investigation into central nervous system involvement is not required). Patients with HTLV1 ATLL and controlled CNS or meningeal involvement may be enrolled after discussion with the MSK principal investigator.
12. The following known cardiac abnormalities:
  - Congenital long QT syndrome.
  - QTc interval  $\geq$  480 milliseconds.
    - A QTc interval between 480-499 msec in the presence of a bundle branch block (BBB) or pacemaker is eligible in phase IIa after discussion with the MSK principal investigator.
  - Myocardial infarction within 6 months of cycle one, day one (C1D1). Subjects with a history of myocardial infarction between 6 and 12 months prior to C1D1 who are asymptomatic and have had a negative cardiac risk assessment (treadmill stress test, nuclear medicine stress test, or stress echocardiogram) since the event may participate.
  - Other significant ECG abnormalities including 2nd degree atrio-ventricular (AV) block type II, 3rd degree AV block.
  - Symptomatic coronary artery disease (CAD), e.g., angina Canadian Class II-IV (see Appendix D). In any patient in whom there is doubt, the patient should have a stress imaging study and, if abnormal, angiography to define whether or not CAD is present.
  - An ECG recorded at screening showing evidence of cardiac ischemia (ST depression of  $\geq$  2 mm, measured from isoelectric line to the ST segment). If in any doubt, the patient should have a stress imaging study and, if abnormal, angiography to define whether or not CAD is present.
  - Congestive heart failure (CHF) that meets New York Heart Association (NYHA) Class II to IV definitions (see Appendix E) and/or ejection fraction <45% by MUGA, echocardiogram, or cardiac MRI.
  - A known history of sustained ventricular tachycardia (VT), ventricular fibrillation (VF), Torsade de Pointes, or cardiac arrest unless currently addressed with an automatic implantable cardioverter defibrillator (AICD).
  - Hypertrophic cardiomegaly or restrictive cardiomyopathy from prior treatment or other causes.
  - Uncontrolled hypertension, i.e., blood pressure (BP) of  $\geq$  170/95; patients who have a history of hypertension controlled by medication must be on a stable dose (for at least one month) and meet all other inclusion criteria.
  - Any cardiac arrhythmia requiring an anti-arrhythmic medication (excluding stable doses of beta-blockers)

13. Patients taking drugs leading to significant QTc prolongation unless able to be switched to non-QTc prolonging medication without risk of worsening underlying condition and meet all other inclusion criteria (listed in Appendix F: Medications That May Cause QTc Prolongation).
14. Concomitant use of significant CYP3A4 inhibitors unless able to be switched to a non-CYP3A4 inhibiting medication without risk of worsening underlying condition and able to meet all other inclusion criteria (listed in Appendix G).

## 7.0 RECRUITMENT PLAN

Potential research subjects will be identified by a member of the patient's treatment team, the protocol investigator, or research team. If the investigator is a member of the treatment team, s/he will screen their patient's medical records for suitable research study participants and discuss the study and their potential for enrolling in the research study. Potential subjects contacted by their treating physician will be referred to the investigator/research staff of the study. Furthermore, eligible patients from the lymphoma or myeloma service will be identified by individual consenting physicians at the time of medical disciplinary rounds or in clinic at Memorial Sloan Kettering Cancer Center, New York Weill-Cornell Presbyterian, Saint Francis/Mount Sinai Regional Cancer Center, and University of Nebraska Medica Center .

